## **Risks to Participants and Adequacy of Protection against Risks**

### Informed Consent

Once individuals express interest in learning more about the study, they will be invited to meet with members of the study team. The general purpose and procedures of this research will be explained to participants, and they will then be given the informed consent document, which will be read aloud; explanations and answers to questions will be given before any testing is undertaken. Along with the official consent form, a supplemental document that utilizes pictures has been developed by the PI to facilitate comprehension of the project procedures and risks for individuals with comprehension impairments secondary to aphasia. Per the criterion listed above, individuals must give evidence of having the linguistic and cognitive capacity to understand the consent form and give informed consent. An Informed Consent Comprehension Screen, adapted from the UCSD Geropsychiatry Research Center, is used with all participants during the consent discussion. Persons with aphasia will be invited to bring to the consent discussion a family member or an individual known to them who is not affiliated with the project. This witness will be encouraged to ask clarifying questions on the individual’s behalf. Given the degree of independence of these community-dwelling stroke survivors, we will not require co-consent from a family member. Consent discussions will take place in a private room and as much time as needed will be allotted to thoroughly explain the study procedures, risks, benefits, confidentiality, and data collection/storage, as well as provide time for the participant to ask questions and have them adequately answered. (Approximately 30-60 minutes).

All PATD-participants will be informed that if evidence of dog abuse (e.g., hitting) or neglect (e.g., severe malnourishment) is observed, they will be withdrawn from the study and reported to Humane Law Enforcement for investigation.

### Behavioral assessments

Anticipated risks are minimal and include fatigue or frustration during the behavioral sessions. To protect against fatigue, participants will be informed they may stop or take a break at any time without penalty. Participants will be invited to take breaks as necessary and reminded that they may cease participation at any time. It is recognized that some participants may demonstrate discomfort while completing the assessments of quality of life. They are informed that some of the questions they will be asked will deal with their personal experiences and emotions related to living with aphasia, and reminded that they may choose not to answer specific questions or may forego this assessment entirely. Participants may also be offered referral information

Assessing an animal-assisted treatment program for adults with aphasia:  
the Persons with Aphasia Training Dogs (PATD) Program

for psychological care, if interested. Risks associated with travel to and from behavioral assessment sessions are anticipated to be not more than those associated with urban daily life.

Dog-training

Risks associated with interaction with dogs include the possibility of physical injury and the risks associated with coming into contact with fur, saliva, waste, or zoonotic disease associated with dogs. Before beginning work with dogs, participants will be provided with guidance on universal precautions. PSPCA participants will receive a pictographic information sheet.

Dogs are screened through either owner-report (for family dogs) or PSPCA behavior staff-report for eligibility. Participants are informed that the program is directed toward training basic obedience skills, not remediation of behavior 'problems', and that the PI conducting the training is not a certified-professional dog trainer. Dogs with a reported history of bites, reactivity (e.g., barking, growling) toward strangers, or resource guarding are excluded. It is anticipated that for participants working with a family dog, risks will not be more than those otherwise experienced in regular interaction with the dog.

Participants interested in working with PSPCA dogs are required to successfully complete the official PSPCA volunteer orientation before beginning the PATD program, hence they must be independently approved by a representative of the PSPCA to be able to work with shelter dogs. Much of the orientation involves hands-on demonstration and practice, making it accessible to individuals with aphasia. Participants interested in volunteering at the PSPCA must demonstrate sufficient mobility and strength to handle a dog. Risks associated with travel to and from the PSPCA are anticipated to be not more than those associated with urban daily life.

Confidentiality

In any research study, there is the risk that personal data will become inappropriately known (risk of loss of confidentiality). Data will be coded with a participant ID number that has no connection with the participant's name or other identifying information. The master list containing the link between the data and the identity will be password protected and accessible only to study personnel. All physical information will be stored in locked drawers in the locked office of the PI or the PI's locked testing room at Moss Rehabilitation Research Institute to which other study staff will have access. Electronic data will be stored on AEHN/TJU networks and/or OneDrive, password-protected computers, , or encrypted external memory devices as appropriate. Data will be removed from the memory storage of the video-recording device as soon as it is practicably possible to transfer it to these systems. Immediately after transfer the videos will be removed from the video-camera storage.

Participants volunteering at the PSPCA will be informed that they are participating in the study in a public venue. PSPCA staff will not be involved in training sessions, and the PI will not identify study participants to PSPCA staff or share participant-specific study information with PSPCA staff. Study staff dog trainers are also PSPCA volunteers and do perform a variety of volunteer work for the PSPCA. They, as are all study staff, are trained in confidentiality via CITI training and review of study documents. There are no completely private spaces within the PSPCA. PATD participants participating at the PSPCA will be informed that it is possible that PSPCA staff or volunteers who see them with the PI or other study staff may surmise that they are PATD program participants, which identifies them as having stroke-aphasia. As participants are also free to discuss their own participation with whomever they choose, they will be informed that the PI cannot guarantee the degree to which their confidentiality will be maintained by third parties. Participants will also be informed that the PI may report to PSPCA staff the identity of the dogs who have worked on each obedience skill. Unedited videos of participants collected during this study may be used for educational purposes (e.g., conference presentations). For video sharing necessary to obtain useful input from others (i.e., to assist the project team in interpreting research information), participant faces will be blurred to maintain participant privacy. The video editing software Davinci Resolve 19 will be used for this purpose.

**Potential Benefits of the Proposed Research to Research Participants and Others**

Assessing an animal-assisted treatment program for adults with aphasia:  
the Persons with Aphasia Training Dogs (PATD) Program

We have found that participants appreciate the time and effort that study personnel take to talk with, as well as the opportunity to discuss, in a supportive environment, the effects of stroke and aphasia on their lives. It is also our experience that many people with aphasia are enthusiastic about the opportunity to contribute to the research evidence-base that could help others with aphasia. All participants will have the possibility of experiencing these benefits. For PATD participants, there is evidence to suggest there are physical and psychosocial benefits of interaction with dogs, and we anticipate there may also be psychosocial benefits to building self-confidence through learning the new skill of dog training. PATD participants may also derive benefit from the knowledge that they are providing enrichment and support to their own dog or to shelter dogs in need. The potential benefits of participation outweigh the possible risks that may be experienced by the individuals who participate.

## Assessing an animal-assisted treatment program for adults with aphasia: the Persons with Aphasia Training Dogs (PATD) Program

### Data and Safety Monitoring Plan

The PI will serve as the Data and Safety Monitor. Study data are accessible to the PI at all times. The PI will maintain regular contact with the CPDTs and SLPs conducting and scoring behavioral assessments. As provided either through narrative interview or extemporaneously by participants, the PI will evaluate participant feedback related to their satisfaction with the program. Participants are free to stop their participation at any time throughout the course of the program. On an ongoing basis, safety associated with working with dogs will be evaluated by the PI, who will revise procedures as needed. Adverse events, including Serious Adverse Events and Unanticipated Problems, will be reported consistent with AEHN IRB procedures,

### Overall Structure of the Study Team

The study team will consist of the PI, the study research assistant (RA), the certified professional dog trainers (CPDT) and the study speech-language pathologists (SLP). The PI will conduct PATD dog probe and training sessions. CPDTs will conduct and review video recordings of the probe and in-person cumulative evaluation sessions, during which the PI will not be present. A second staff member may be present during all PATD sessions to video-record the sessions. The RA may assist with recruitment, scheduling, and data collection (including video recording) and analysis. One SLP will conduct behavioral assessment sessions and a second SLP will score study instruments and code video-recordings of narrative interviews.

### Statistical Design and Power

For this feasibility study, we anticipate enrolling a minimum of twenty participants with stroke-aphasia.

Scores from weekly probes will allow for analysis of change in level of 'competence' over time, as determined using the *PPAHE* for that skill. For the purpose of statistical analyses of weekly evaluations, three scores (0="not ready", 1="ok", 2="best") will be dichotomized as competent (1 or 2) vs. not competent (0). In addition to the weekly evaluations, at the end of the training period, each participant will receive a summative score on the adapted *PPAHE*. This score may range from 0 to 10. For the primary analysis, the proportion of subjects that successfully completed the training will be quantified with the corresponding two-sided 90% exact binomial confidence interval. For the secondary analysis, (i) the median cumulative score will be computed with the corresponding two-sided 90% distribution-free confidence interval (Hahn & Meeker, 2011) and (ii) the weekly competence scores will be analyzed using the repeated measures logistic regression model. With the total sample size of 20 subjects, the width of the two-sided 90% exact binomial confidence interval is at most 0.38 if the observed proportion of subjects successfully completed the training is 0.5. The interval is narrower if the observed proportion of successes is higher (or lower) than 0.5.

The mean pre-to-post-training change in each ALA domain scores will be computed with the corresponding 90% confidence interval. With the total sample size of 20 subjects, the width of the two-sided 90% confidence interval is equal to 0.39 standard deviations of the pre-to-post-training changes. For the secondary analysis, we will evaluate the mean difference in each ALA domain scores between the immediate and delayed treatment arms at week 7 using the two-sided 90% confidence interval and two-sided two-sample t-test with alpha 0.1 (reflective of the small size pilot study). The results of comparison between the immediate and delayed treatment arms will be used to inform future larger studies. Qualitative data derived from narratives produced by PWA during administration of the PATD ALA-supplement will be orthographically-transcribed for offline analysis of themes discussed consistent with procedures detailed by Luck & Rose, 2007.

To the extent that variation across the sample allows, we will explore the effects on performance of demographic (age, education) and aphasia-related (time post-onset, *WAB-R AQ*) variables. Due to the nature of the differences between PATD participation with a family dog and with shelter dogs, we will not run between-group analyses of PATD versus PATD-PSPCA participant groups.

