
## Assessing an animal-assisted treatment program for adults with aphasia: the Persons with Aphasia Training Dogs (PATD) Program

**Skills Training:** In consultation with a certified professional dog trainer, the PATD program was developed by the PI, a trained speech language-pathologist with more than eighteen years of experience working with people with aphasia, who has spent more than ten years working with shelter animals using positive reinforcement techniques.

Participants enrolled in the PATD program will engage in five once-weekly individual training sessions with the PI, either with a family dog (PATD) or by volunteering at a local shelter, the Pennsylvania SPCA (PATD-PSPCA). PATD-PSPCA participants will work only with dogs that have been evaluated by PSPCA staff as appropriate for interaction with new volunteers. Each session will be dedicated to one of five pre-determined, sequentially-presented, obedience skills (i.e., LOOK, TOUCH, SIT, STAY, COME). Training sessions will last approximately 75 minutes, with an additional half hour allotted to the beginning of the first training session to review principles of positive-reinforcement training. Subsequent sessions will begin with a brief probe of the participant's skill in cueing the dog to perform the behavior trained the previous week. Following the probe, sessions will continue with a review of that week's lesson plan (Figure 1), after which the PI will model the first training step three times. After the model has been provided, the participant will attempt the procedure, receiving instructive feedback or reinforcement from the trainer. Instruction will proceed to the subsequent step when the participant and dog have attained 5 successful trials at the current step. The same demonstration procedure will be used at each subsequent step. Commands will be trained using one hand gesture for each behavior. To mark behaviors, participants will use a clicker attached to a wrist band, which can be hand-held or allowed to dangle for ease of use for those with hemiplegia. Participants will have the option of introducing the verbal command, but will not be required to do so. All participants will be asked to provide their dog with a walk before training sessions to support the dog in being ready to participate.

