**Skills Practice:** Participants will not be required to complete all steps for an obedience skill in a single session, and will be encouraged to practice the skill with the dog for at least 3 practice sessions over the course of the week. Practice will be used as a measure of participant compliance. Each participant will be provided with a copy of the lesson plan and, if interested, a video demonstrating the PI performing the target skill with her own dog. Participants will also be provided with a training log to complete after each time they practice over the course of the week. Using a nine-point visual analog scale adapted from the *Assessment of Living with Aphasia* (ALA) (Simmons-Mackie et al., 2014), participants will rate their own and the dog's performance during each practice session (see *PATD Practice Log*, in Appendix). To facilitate responses on the log, participants will practice self-reflection with the PI during training sessions (e.g., "How many times did I have to cue the dog?", "Did I 'click' as soon as the dog did what I asked?").

**Skills Evaluation:** In consultation with a CPDT who is a practitioner of positive reinforcement training, the PI-adapted *Pet Partners® Animal-Handler Evaluation (PPAHE)* will be used to evaluate handler competence, on parameters associated with shaping and timing, on a scale of 0 ("not ready") to 2 ("best") (see blank *PPAHE* in Appendix). Weekly single-skill probes will be conducted by the PI/trainer but will be scored via video-recording by a certified professional dog trainer (CPDT). Summative assessment of all skills will occur twice, within one week of training completion and at a 3-month follow-up. Summative assessments will be completed in person by a CPDT who will also score the weekly formative evaluations via video-recording. To maintain scientific rigor, the CPDT will score probe evaluations via video after the follow-up in person summative evaluation has been completed. As reflected in the adapted *PPAHE*, scores will be based solely on participants' competence

**MossRehab Aphasia Center  
PATD Program**

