## Assessing an animal-assisted treatment program for adults with aphasia: the Persons with Aphasia Training Dogs (PATD) Program

using the positive reinforcement techniques, not on the performance of the dog. Dogs' behaviors in response to cuing are noted to provide for qualitative assessment of the participant's responsivity to the dog and so that relief (e.g., break for walk or play) may be immediately provided to the dog if signs of stress, fatigue, etc. are observed.

**Statistical Considerations:** Scores from weekly probes will allow for analysis of change in level of 'competence' over time, as determined using the *PPAHE* for that skill. For the purpose of statistical analyses of weekly evaluations, three scores (0= "not ready", 1= "ok", 2= best") will be dichotomized as competent (1 or 2) vs. not competent (0). In addition to the weekly evaluations, at the end of the training period, each participant will receive a summative score on the adapted *PPAHE*. This score may range from 0 to 10. In keeping with our a priori hypothesis that participants will be able to independently cue a dog to perform a minimum of 4 out of 5 obedience behaviors, a score of 5/10 points corresponds with achieving a minimum of a 1 ("ok") on all five targeted obedience behaviors or achieving a 2 ("best") on at least one behavior and 1 on three others. For the primary analysis, the proportion of subjects that successfully completed the training will be quantified with the corresponding two-sided 90% exact binomial confidence interval. For the secondary analysis, (i) the median cumulative score will be computed with the corresponding two-sided 90% distribution-free confidence interval (Hahn & Meeker, 2011) and (ii) the weekly competence scores will be analyzed using the repeated measures logistic regression model. With the total sample size of 20 subjects, the width of the two-sided 90% exact binomial confidence interval is at most 0.38 if the observed proportion of subjects successfully completed the training is 0.5. The interval is narrower if the observed proportion of successes is higher (or lower) than 0.5.

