Participants enrolled in the PATD program will engage in five approximately once-weekly individual training sessions with the PI, either with a family dog (PATD) or by volunteering at a local shelter, the Pennsylvania SPCA (PATD-PSPCA). Each session will be dedicated to one of five pre-determined, sequentially-presented, obedience skills (i.e., LOOK, TOUCH, SIT, STAY, COME). Training sessions will last a maximum of 75 minutes, with an additional half hour allotted to the beginning of the first training session (before the dog begins participation) to review principles of positive-reinforcement training. Sessions may last for fewer than 75 minutes if a) criterion is achieved, b) human or dog participant demonstrates fatigue, loss of attention, etc. Subsequent sessions will begin with a brief probe of the participant's skill in cueing the dog to perform the behavior trained the previous week. Following the probe, sessions will continue with a review of that week's lesson plan, after which the PI will model the first training step three times. After the model has been provided, the participant will attempt the procedure, receiving instructive feedback or reinforcement from the trainer. Instruction will proceed to the subsequent step when the participant and dog have attained 5 successful trials at the current step. The same demonstration procedure will be used at each subsequent step. Commands will be trained using one hand gesture for each behavior. To mark behaviors, participants will use a clicker attached to a wrist band, which can be hand-held or allowed to dangle for ease of use for those with hemiplegia. Participants will have the option of introducing the verbal command, but will not be required to do so. All participants will be asked to provide their dog with a walk before training sessions to support the dog in being ready to participate. The PI will demonstrate the steps of the obedience training and will be present for the entire training session to observe, assist, and provide feedback to participants. Within the framework above, treatment will be individualized for each participant-handler/dog pairing based on real-time clinical decision-making. One goal of positive reinforcement training is relationship building between the particular handler/dog pairing. Reinforcement, redirection, and feedback will be provided by the PI, who will complete all training sessions, based on the individual needs of the human and dog participants. Participant handlers will be provided with feedback regarding their use of shaping, timing of cues and rewards in real time and lesson plans will be modified as needed for each individual. Examples of lesson plan modifications include training in use of one hand for those with hemiplegia or increased white space or font size or additional pictographs for those with reading difficulty.

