
Participants will be encouraged to practice the skill in 3 practice sessions over the course of the week. Participants will be instructed that each practice session should not last longer than approximately 30 minutes and that breaks for play, drinking water, sniffing-walks, should be provided as needed. Practice sessions may also be broken up into shorter increments (e.g., three 10-minute sessions, six 5-minute sessions). Practice will be used as a measure of participant compliance. PATD-participants will be provided with aphasia-friendly written materials including: 1) lessons plans, 2) practice log sheets, and 3) practice reminders. They may also be provided with example videos of the PI performing the obedience skills with her own dog. PATD-participants will be informed that at the beginning of the subsequent training session, the PI will be evaluating their ability to cue the behavior introduced the previous week using a PI-adapted *Pet Partners® Animal-Handler Evaluation*

Assessing an animal-assisted treatment program for adults with aphasia:  
the Persons with Aphasia Training Dogs (PATD) Program

(adapted *PPAHE*) will be used to rate handler cueing on a scale of 0 (“not ready”) to 2 (“best”). Progression to training of each behavioral skill will not be contingent on evaluation of the previous skill.

After each training session, the participant will be provided with a copy of the appropriate lesson plan, three participant practice logs, and, if interested, a video demonstrating the PI performing the target skill with her own dog. As study staff will not be present for practice sessions, participants will be instructed on behaviors to watch for that indicate the dog might need/want a break or to stop practice for the day, e.g., signs of fatigue (e.g., inattention, disinterest in interaction) or distress (e.g., tail tuck, ears flat/back, avoidance). PSPCA participants will be instructed to practice with the same dog with whom they trained on each skill. If that dog is not available, they will be instructed to work with another dog who has been labeled by PSPCA staff to be at (or easier than) their current level of proficiency as determined by the PSPCA (e.g., beginner volunteers may only work with beginner-appropriate dogs).

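### Weekly probes test each skill once, in a fixed order, so a trend across weeks cannot be read as change in competence over time

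*Combined protocol and SAP*

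**What the plan says.** The relevant text is in the combined protocol and SAP.

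- **Stated purpose.** Statistical Design and Power, repeated in the Statistical Considerations paragraph under Specific Aim 1: "Scores from weekly probes will allow for analysis of change in level of 'competence' over time, as determined using the *PPAHE* for that skill". Scores of 1 or 2 count as competent and 0 as not competent.
- **Model.** Secondary analysis (ii): "the weekly competence scores will be analyzed using the repeated measures logistic regression model". The coding of time, any skill term and the quantity to be estimated are not given.
- **Order of training.** Skills Training: "Each session will be dedicated to one of five pre-determined, sequentially-presented, obedience skills". The order listed is LOOK, TOUCH, SIT, STAY, COME.
- **Content of a probe.** Skills Evaluation: "Weekly single-skill probes will be conducted by the PI/trainer". Study Procedures and Materials says that each session after the first opens with a probe of skill "in cueing the dog to perform the behavior trained the previous week".
- **Progression.** Study Procedures and Materials: "Progression to training of each behavioral skill will not be contingent on evaluation of the previous skill".
- **What is scored.** The adapted PPAHE is used to "evaluate handler competence, on parameters associated with shaping and timing". Scores rest on the participant's competence "using the positive reinforcement techniques, not on the performance of the dog".

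All skills are rated together only at the two summative assessments. These are analysed separately, as a success proportion and a median cumulative score.

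**The concern.** To measure change in competence over time, either the same thing must be measured more than once, or different things must be measured on a scale known to be comparable across occasions. The weekly series does neither. Week 1's skill is never probed again within the series, and no statement says that the skills are comparable in difficulty along the order. No re-probe, pre-training probe or counterbalancing is described.

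A report could therefore present a rising week trend as learning when the later skills were simply easier to cue. It could equally present a flat trend as no learning when rising difficulty had cancelled real gains. The study is meant as the foundation for a larger trial, so either misreading could be carried forward.

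**Working it through.** The plan gives no sample size, power or effect size for this analysis, so there is no figure to reproduce. The question is whether the design can identify the effect.

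**Inputs from the documents.** Five skills, one per session, in one order for both arms (Skills Training; Table 1). Probes come at the start of sessions 2 to 5, each on the previous week's skill. Minimum 20 participants.

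**Number of scores.** Probes per participant = 5 − 1 = 4 (LOOK, TOUCH, SIT, STAY; no weekly probe of COME is described). Total = 4 × 20 = 80 if complete. The count of four is inferred from the session description.

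**Aliasing.** Week k always carries skill k.

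| Terms in the model | Columns | Rank |
|---|---|---|
| Intercept + linear week + 3 skill indicators | 5 | 4 |
| Intercept + 3 week indicators + 3 skill indicators | 7 | 4 |

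Adding week to skill adds no information. With five probes the result is the same: five skill indicators plus week have rank 5 of 6. Randomization to waitlist does not help, because both arms use the same order: skill + arm + study week has rank 5 of 6 with four probes.

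If week is fitted as a factor, the model is simply competence by skill. If week is fitted as a line, then on the log-odds scale

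week slope = learning per week − increase in difficulty per week,

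and the probes cannot separate the two parts.

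**How large the error could be (assumed values).** Assume no learning and four skills whose competence falls in equal steps. Fit the large-sample logistic slope on weeks 1 to 4 for all 24 orders of the skills. Odds ratios are exp(−slope) and exp(slope).

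| Competence range | Worst slope | Worst odds ratio | Median slope | Median odds ratio | Orders with odds ratio ≤ 0.80 or ≥ 1.25 |
|---|---|---|---|---|---|
| 0.85–0.75 | 0.210 | 0.81 or 1.23 | 0.083 | 0.92 or 1.09 | 0 of 24 |
| 0.90–0.70 | 0.433 | 0.65 or 1.54 | 0.168 | 0.85 or 1.18 | 10 of 24 |
| 0.95–0.65 | 0.685 | 0.50 or 1.98 | 0.253 | 0.78 or 1.29 | 18 of 24 |

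For each range, 2 of the 24 orders (the monotone ones) give the worst value and 2 give an odds ratio of 1.00.

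Equal difficulty is not required. Competence of 0.70, 0.90, 0.90, 0.70 in weeks 1 to 4 gives a slope of 0. What matters is a trend along the order.

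**Scale against sampling error.** With 20 people, 0.80 competent and independent probes (assumed), the sum of squared deviations of weeks 1 to 4 is 5, so

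SE = √(1 / (20 × 0.80 × 0.20 × 5)) = √(1/16) = 0.25.

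For the 0.90–0.70 range, the median-order error of 0.17 lies within sampling noise. The monotone error of 0.43 is not small against it.

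**Simulation of the planned type of model.** Logistic GEE, 20 participants, 4 probes, two-sided alpha 0.10, 500 runs per case. Assumed: first-probe log-odds 1.0, participant SD 1.0, and slopes of 0 or 0.5 log-odds per week.

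| Learning per week | Difficulty per week | Median week slope | Rejections |
|---|---|---|---|
| 0 | 0 | 0.00 | 11% |
| +0.5 | 0 | +0.43 | 58% |
| 0 | −0.5 (easier) | +0.46 | 56% |
| +0.5 | +0.5 (harder) | 0.00 | 12% |
| 0 | +0.5 (harder) | −0.44 | 76% |

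True learning cannot be told from skills getting easier. Learning offset by rising difficulty cannot be told from no effect.

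**The case against.** The best defence is that the plan never uses the word learning for this analysis. It attaches no hypothesis, expected trend or decision to it, and the expected results cover only the four-of-five criterion and the median summative score. On that reading, the model describes how often handlers are rated competent at successive stages of the program, on one shared construct. Because the handler's shaping and timing are scored and not the dog's performance, skill differences may be small. A model with week alone, or skill alone, is full rank; the rank deficiency arises only if both are entered. The phrase about the PPAHE for that skill may only say how each score is obtained. Finally, every bias figure rests on assumed spreads. For the 0.90–0.70 range, 14 of 24 orders give a bias below the 0.25 standard error, and with five probes the worst odds ratios fall to 1.17, 1.38 and 1.66.

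Much of this stands. Fitting a clustered logistic model is not an error, the consequence may be nil, and this is a secondary analysis in a feasibility study. But the text promises analysis of change over time, and readers will take a week trend in competence as growth. Handler-based scoring may shrink differences between skills; nothing in the documents shows that it removes them. The rank result does not fault a proposed model. It shows that no model of these scores alone can separate the two explanations. Dog changes in the shelter stratum and dropout can also move a week trend, which weakens the over-time reading further.

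**Conclusion.** The concern holds. The weekly probes, as described, do not have the property claimed for them: week and skill are exactly aliased, whether there are four probes or five. That conclusion rests only on the documents' own description of order and probing.

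The practical size is unknown. The odds ratios above depend on assumed competence levels and orders, and the true error may be zero. The problem lies in the over-time interpretation, not in fitting a repeated measures logistic model. The primary proportion, its interval, the median summative score and Hypothesis 1 are untouched. The wording should be corrected, but the trial's main conclusion does not depend on it.

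**What to change.** In both Specific Aim 1 (Statistical Considerations) and Statistical Design and Power, replace the sentence on change over time with text such as:

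> Weekly probe scores will describe competence on each skill at the session after it was trained. Because each skill is probed once, in a fixed order, differences between weeks will not be interpreted as change over time.

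For secondary analysis (ii), report competence by skill, as proportions or from the clustered logistic model with skill as a factor, and label it descriptive. Alternatively, keep the week trend, state the assumption of no difficulty trend along the order, and make no claim of learning.

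An optional, exploratory addition is to compare each of LOOK to STAY between its probe and the two summative assessments, which are already collected. Adding those ratings makes skill + week estimable (rank 6 of 6). The comparison would need these caveats:

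- Scoring mode, presence of the PI, the dog (shelter participants) and possibly the rater differ between occasions.
- Probes are scored after the follow-up summative assessment.
- The lag from probe to post-training evaluation is tied to skill: 7 − 3, 7 − 4, 7 − 5 and 7 − 6, or about 4, 3, 2 and 1 weeks.
- A main-effects model assumes no skill-by-occasion interaction, and ceiling effects and dropout may limit it.

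Skills Evaluation and Scientific rigor under Specific Aim 1 disagree on whether one CPDT scores both probes and summative assessments. They should be reconciled before any such comparison.

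The cost is a wording change in two places and a relabelled table, with no new visits, probes or scoring. The price is a narrower secondary conclusion: competence by skill, not growth over time.
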